- e. Because there is variation in how clinicians approach preventing harms from opioids, ISOT will take a flexible approach to accommodate clinician preferences; we will collect information about PACT team preferences for communication with the intervention team and opinions on opioid prescribing and monitoring prior to initiating the study.⁵³ The NCM will provide feedback to each PACT team member in a manner consistent with preferences (i.e., discussion, chart note, secure email, voicemail message, etc.).
- f. An email list serve (using encryption and within security firewall), managed by the PCP pain specialist and substance abuse psychologist, will be used to communicate information and facilitate dialogue among intervention clinicians. In our prior research, clinicians appreciated the opportunity to discuss (non-identifying) patient management strategies.

Patient Assessment and Activation:

- a. The NCM will perform a chart review of each ISOT patient and schedule a one-time appointment.
- b. With each patient, the NCM will review strategies for increasing opioid safety and discuss adverse effects of prescription opioids, including overdose, falls, interactions with other medications or alcohol/illicit substances, and opioid withdrawal. The NCM and patient will discuss treatment goals, options, and self-management approaches. Supplemental written materials will describe risks and benefits of opioids. With PCP authorization, the NCM will facilitate completion of opioid treatment agreements, as needed.
- c. The NCM will talk with patients about the rationale behind screening for adherence to prescription opioids with UDTs, and focus on patient safety and risk-benefit of opioids.⁷⁶
- d. Patients will receive information about common ways in which opioids are diverted (e.g., taken by friends or family, loaning to others) and potential harms associated with diversion. Recommendations will be provided about methods for limiting opioid diversion, including details about medication take-back programs.
- e. Patients will be provided with an easy-to-read brochure that describes adverse effects of opioids, methods for reducing the likelihood of adverse events, rationale for prescription opioid abuse screening, and strategies for preventing diversion.

System Assessment and Intervention:

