- a. The NCM will maintain a registry of all enrolled patients and track UDT administrations. For patients that have not been administered a UDT in 12 months or more, the NCM may assist the PCP by placing an order for UDT in the medical record.
- b. The NCM may write the UDT order for the PCP to sign, if requested. The NCM will recommend checking state PDMP data for patients without a past-year check. (In Oregon, only prescribers are authorized to check PDMP data, so the NCM could not query the database him/herself.) PDMP checks are recorded in the medical record, so the research team will be able to track frequencies. If requested, the NCM may collaborate with pharmacy services to query state PDMP databases.
- c. The NCM will provide support about methods for talking with patients about prescription opioid adherence monitoring. This will include providing written information, such as scripts that clinicians can follow. In pilot interviews, PCPs requested these types of materials to assist with improving adherence to opioid regimens.
- d. The NCM will track all UDTs, notify the PCP of the results, and provide recommendations

about potential next steps in care. With collaboration from the primary care pain specialist and substance abuse specialist, the NCM will provide decision support to clinicians for patients with prescription opioid abuse about options for modifying treatment. The NCM will also follow-up to ensure treatment recommendations are implemented.

- e. With input from the NCM, some patients may be referred for supplemental treatment. This may include referral to the substance abuse treatment program, mental health clinic, or specialty pain service.
- f. The NCM may identify potential side effects or risky prescribing practices that have not been addressed.

Follow-up: Participants will complete assessments at baseline, 6 months, and 12 months post-baseline. During research visits, participants will complete all study measures, the structured clinical interview, and provide a UDT.

In the course of the study, a PCP or PACT nurse who is enrolled in the study may leave their position at the Portland VA. Clinical patients who are “attached” with these clinicians and already enrolled in the study will remain eligible to participate. Clinical recommendations that are made regarding patient’s care will continue to be forwarded to PACT team members who remain involved in each patient’s treatment.

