Participants will also be reimbursed for their participation. This includes a \$50 payment for each of the three research visits. This reimbursement amount is intended to cover time to complete the research visit and/or costs of travel to and from the hospital for the visit. This payment amount is consistent with other research studies of similar duration and intensity and do not appear to put undue pressure on prospective subjects to participate. The payment amount and terms of payment are specified in the consent form.

Study Measures: Research staff collecting outcome data will be blinded to participant and clinician intervention status. The ISOT intervention team will not have access to data obtained by the research team, except if a patient’s safety becomes a concern.

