Measures of Prescription Opioid Misuse/Abuse (Aim 1): The primary outcome will be responses to the Current Opioid Misuse Measure (COMM), a 17-item self-report measure that assess several constructs that place individuals at risk of opioid misuse and abuse.⁸⁰ The COMM has been well-validated⁸¹ and previously used in treatment outcome studies.³³ The COMM has also been validated for detecting prescription opioid abuse using cut-off scores ≥ 13 .⁸² The Timeline Followback (TLFB; Sobell & Sobell, 1992) is a frequently used assessment method that uses calendar prompts to elicit frequency and intensity of substance use within a specific timeframe. The TLFB has demonstrated good test-retest reliability and validity for assessing multiple substances at one time (Ehrman & Robbins, 1994; Fals-Stewart et al., 2000). This study will assess use of alcohol, marijuana, methamphetamine, cocaine, heroin, opioid medications, and other prescription medications in the past 30 days. The Structured Clinical Interview for DSM-IV(SCID) will be used to assess current alcohol and substance use disorders.⁸³ The Overdose Risk Behavior (ORB) questionnaire is a newly-developed 14-item self-report measure that assesses behaviors and activities that place an individual at higher risk of accidental overdose to prescription opioids. Participants will complete Urine Drug Tests, to evaluate for the presence of substances ingested by participants. UDTs will evaluate for cannabis, cocaine, amphetamines, benzodiazepines, barbiturates, opioids, and opiates. Confirmatory testing will be conducted for all UDT screens with unexpected results. The purpose of UDT is to have confirmation of certain prescribed and illicit substances that have been ingested by study participants. Research staff will review medical record data prior to research visits to confirm medication status. Participants will be asked to validate pharmacy data about prescription status, as well as medications prescribed outside VA.

Measures of Opioid-Related Adverse Events (Aim 1): Prior to appointments, research staff will review medical record data for participants to track adverse effects. This includes emergency room visits, falls, and overdoses. Participants will also be queried about these effects and motor vehicle accidents at each research visit.

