observations on different patients of the same PCP and for repeat observations on the same patient. Transformations of the outcome will be applied to meet distributional assumptions. In linear mixed models, we will include baseline measures of patient age, sex, depressive symptoms, history of SUD, and pain severity as covariates. We will also adjust for baseline COMM score and the stratification variables: PCP training type (MD/DO vs NP or PA) and proportion of clinician panel prescribed opioids (high vs low). In addition to testing formal hypotheses, we will report 95% confidence intervals for the differences in mean outcomes between groups at 6 and 12 months. For comparing the percentages classified as abusing opioids at any time during follow-up (combining information from 6 and 12 months) based on SCID and UDT, we will use generalized-linear mixed models (or GEE as needed) to incorporate correlation between patients of the same PCP. We will adjust for baseline measures of the outcome along with the covariates listed above. We will report group comparisons on all three primary outcomes (COMM, SCID, and UDT). Assuming 15% of the sample has current SUD (consistent with other research), we will not conduct interaction analyses, but will present descriptive information for each outcome (COMM, SCID, UDT) on treatment outcomes by SUD status.

Data on opioid-related adverse events will be obtained from the medical record and participant self-report. We will collect data on opioid overdoses, falls, motor vehicle accidents, and ER visits related to pain. Descriptive information on opioid-related events will be provided for each group (numbers and percentages of participants with each event). Because the number of adverse events is expected to be small, we will use Fisher's Exact test to compare adverse event percentages between groups. We will compare both percentages for each individual type of event as well as percentages of individuals experiencing any adverse event between groups.

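### Falls and overdoses may be over-ascertained in the ISOT arm, because the intervention adds surveillance that can feed one of the two adverse-event sources

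*Combined protocol and SAP*

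**What the plan says.** Specific Aims, Aim 1 Hypothesis 2, predicts fewer ER visits, overdoses, falls and motor vehicle accidents in ISOT patients at 12 months.

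Two sources supply these events in both arms. Under Measures of Opioid-Related Adverse Events (Aim 1): "Prior to appointments, research staff will review medical record data for participants to track adverse effects". On the events sought there: "This includes emergency room visits, falls, and overdoses". The second source is the participant: "Participants will also be queried about these effects and motor vehicle accidents at each research visit". Analyses for Aim 1 uses both: "Data on opioid-related adverse events will be obtained from the medical record and participant self-report". Percentages for each event type and for any event are then compared by Fisher's exact test. No rule for combining the sources, analysis by source or adjudication is described. Study Measures states: "Research staff collecting outcome data will be blinded to participant and clinician intervention status".

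The ISOT arm has these additions:
- Patient Assessment and Activation, items a and b: the NCM reviews each ISOT patient's chart and holds one appointment to "discuss adverse effects of prescription opioids, including overdose, falls, interactions with other medications" and other topics.
- System Assessment and Intervention, item f: "The NCM may identify potential side effects or risky prescribing practices that have not been addressed".
- Clinician Education and Activation, item e: feedback to the care team follows each member's preference, and a chart note is one of the listed routes.

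The last paragraph of Background, before Research Design and Methods, says that the study intervention will raise the amount of checking for adverse effects. No NCM or equivalent contact is described for control patients.

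**The concern.** An outcome source should not be altered by the treatment under test. Here the clinical record is both a place where the intervention may leave traces and a source for the outcome. If a fall or overdose is more likely to be written down because a nurse is following the patient, the same true event rate gives a higher observed rate under ISOT. Blinding the extractors does not correct this, since they can only extract what was recorded.

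The bias runs against Hypothesis 2. It could hide a real reduction or create an apparent harm, so neither a null nor an adverse result could be read with confidence.

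The plan avoids the parallel problem elsewhere. ISOT prompts more clinical urine drug tests, and Processes of Care Measures (Aim 2) rules out clinical tests as an outcome for opioid abuse, using research tests given to everyone instead. Adverse events have no comparable safeguard.

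A second issue is related. Staff review the record before the visit at which they ask about the same events. An NCM-authored note seen then could reveal the arm before the question is put.

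**Working it through.** The plan gives no adverse-event rate, power or detection figure to reproduce. It says only that the number of events should be small. The calculation below is therefore an illustration.

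**From the plan.** 32 PCPs per group × 5 patients = 160 patients per arm.

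**Assumed.**
- True event rate equal in both arms: 10%, 20% or 30%.
- Record sensitivity: 0.4 in control; 0.6 or 0.8 in ISOT.
- Self-report sensitivity: 0.5, 0.7 or 0.9, the same in both arms.
- The two sources detect independently, and an event counts if either finds it.
- Clustering is ignored.

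**Formula.** Combined detection = 1 − (1 − record)(1 − self-report). Observed rate = true rate × combined detection. With equal true rates, the spurious ratio is the ratio of the two combined detections and does not depend on the true rate.

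**Worked case** (true rate 20%, record 0.4 vs 0.6, self-report 0.7):
- Control: 1 − 0.6 × 0.3 = 0.82; observed 0.20 × 0.82 = 16.4%.
- ISOT: 1 − 0.4 × 0.3 = 0.88; observed 0.20 × 0.88 = 17.6%.
- Ratio 0.88 / 0.82 = 1.07; spurious excess 1.2 points.

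The last column gives the chance that a two-sided Fisher test at 0.05, with 160 per arm, finds ISOT significantly worse (exact enumeration).

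| Record, control / ISOT | Self-report | Combined, control / ISOT | Ratio | Chance at true 10% / 20% / 30% |
|---|---|---|---|---|
| 0.4 / 0.6 | 0.5 | 0.70 / 0.80 | 1.14 | 3.4% / 5.3% / 7.3% |
| 0.4 / 0.6 | 0.7 | 0.82 / 0.88 | 1.07 | 2.5% / 3.4% / 4.3% |
| 0.4 / 0.6 | 0.9 | 0.94 / 0.96 | 1.02 | 1.9% / 2.2% / 2.5% |
| 0.4 / 0.8 | 0.5 | 0.70 / 0.90 | 1.29 | 6.7% / 12.8% / 20.2% |
| 0.4 / 0.8 | 0.7 | 0.82 / 0.94 | 1.15 | 3.9% / 6.2% / 8.8% |
| 0.4 / 0.8 | 0.9 | 0.94 / 0.98 | 1.04 | 2.2% / 2.7% / 3.3% |

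With equal record sensitivity (0.4 in both arms) and the same self-report values, the chance is 1.5% to 1.9%.

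**How much self-report dilutes.** From the record alone, the ratio would be 0.6 / 0.4 = 1.50 or 0.8 / 0.4 = 2.00, and the chance of a falsely significant harm 8% to 77%. Adding the common query brings these down to 1.02 to 1.29 and 2% to 20%.

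**Masking a real benefit** (true 30% control vs 20% ISOT, self-report 0.7):
- Equal record sensitivity of 0.4: observed 24.6% vs 16.4%; chance of a significant benefit 39%.
- Record 0.4 vs 0.6: observed 24.6% vs 17.6%; chance 29%.

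**If events are rarer.** At an assumed 5% rate, the worked case gives 0.05 × (0.88 − 0.82) = 0.3 points, or 0.003 × 160 = 0.5 patient. The widest case gives 0.05 × (0.90 − 0.70) = 1.0 point, or 1.6 patients.

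**The case against.** A reader might infer that falls and overdoses are simply taken from the chart, that the NCM asks about and charts them, and that they are therefore over-counted under ISOT. The documents do not support that reading:
- Participants in both arms are asked about these events at every research visit, by staff intended to be blinded. An event the participant already reports adds nothing to a per-participant percentage when the chart also holds it.
- No section tells the NCM to take or record a history of past falls or overdoses. The appointment covers them as risks; item f of System Assessment and Intervention says only that side effects may be identified and names no charting; a chart note is one optional feedback route. The ongoing record monitoring in Clinician Education and Activation, item d, is directed at non-adherence.
- Clinicians in both arms attend the workshop, whose topics include screening for adverse effects.
- Every sensitivity and event rate above is assumed, and with rare events the absolute bias is a patient or two.
- Hypothesis 2 lies outside the three outcomes the analysis section calls primary (COMM, SCID and urine drug tests). Motor vehicle accidents come from the query, and ER visits arise from a care encounter, so those comparisons are probably little exposed.

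All of this stands, and it limits the point to a risk of unknown size, mainly for falls and overdoses. It does not remove the point. The workshop narrows the difference between arms, but the NCM works in one arm only, and the protocol itself expects ISOT to raise checking for adverse effects.

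A further objection concerns remedies. Deleting events from ISOT charts alone would tilt the comparison toward ISOT. Relying on the query and ER records alone would lose fatal overdoses without an ER encounter, and non-ER events in participants who miss visits. Nor is the query perfectly neutral, since ISOT patients are taught about these events. The fix has to respect these limits.

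**Conclusion.** The concern holds as a risk of differential ascertainment, not as a demonstrated over-count. One of two adverse-event sources can be enriched by the intervention in one arm, the plan does not separate the sources, and blinded extraction cannot repair a difference in what is recorded. The likely direction is against Hypothesis 2.

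The size cannot be derived from the documents. Under the assumed inputs the spurious ISOT/control ratio is about 1.02 to 1.29, and the chance of a falsely significant harm is 2% to 20%, against just under 2% with equal ascertainment. The upper ends need record sensitivity to double under ISOT while self-report finds only half of events; if self-report finds most events, the bias is slight. These figures also rest on equal self-report in both arms, independence of the two sources and no clustering.

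The change is worth making because it is cheap and decides whether a null or adverse result on Hypothesis 2 can be interpreted.

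**What to change.** - Flag the source or sources of each event: visit query, ER encounter, other record entry, NCM-authored note.
- Keep the planned all-source comparison. Beside it, prespecify a between-arm comparison restricted to the visit query and ER encounters, which are collected alike in both arms.
- Report record-only events by arm, and list separately those known only from NCM-authored notes.
- Keep fatal overdoses from any source in both comparisons.
- Do not try to exclude entries that other clinicians made after an NCM prompt. They cannot be identified reliably, and removing them would act on one arm only.
- Have blinded staff skip NCM-authored notes when they review the record before a visit. Someone outside the blinded assessor role extracts those notes afterwards.

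The cost is analysis-plan wording, one source field per event and slightly more extraction work. The restricted comparison loses some true non-ER events, including those in participants who miss visits, which is why it accompanies the all-source comparison and does not replace it.

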During the screening telephone call, the study research assistant will provide a brief overview of the study purpose (including clear statements that participation involves research and participation does not provide clinical treatment), review inclusion/exclusion criteria, describe what participation in the study would entail, and schedule participants for a study appointment session. If the patient is interested in participating and eligible, the patient will be scheduled for a baseline assessment (participants will also receive reminder phone calls and/or letters prior to their scheduled appointment). To enhance the likelihood of participants attending the study evaluation session, we will offer a \$50 payment in compensation for time and/or travel to attend the research visit. The baseline assessment and all follow-up evaluations will be conducted either in person or via telephone.

During the telephone screening visit, if the participant is ineligible, but is interested in receiving additional clinical services, s/he will be referred to the study PI to contact for information about relevant clinical resources.

During the assessment sessions, the research assistant will provide another overview of study participation, administer informed consent and HIPAA authorization, and instruct the participant to complete study measures.

Follow-up: In addition to the baseline assessment, all participants will complete follow-up assessments every 6 months. During these research visits, participants will complete all study measures (described below). Research visits must be completed within 1 month of the scheduled follow-ups (i.e., the 6-month follow-up must be completed between 5-7 months from baseline and the 12 month follow-up must be completed between 11-13 months from baseline).

Randomization: We will randomize by PCP; patients will be assigned to intervention or control based on randomization of their PCP and PACT nurse. At the VAPORHCS, each PACT nurse is assigned to a single PCP and each PCP has one PACT nurse. Thus, contamination effects by PACT nurses working with a PCP assigned to the control condition will not be a concern.

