We will randomize dyads of PCPs and PACT nurses to receive ISOT versus control. We will initially recruit PCPs to participate. Of the PCPs who choose to enroll, we will then attempt to recruit the PACT nurse who is assigned with that PCP (if the PACT nurse chooses not to participate, the consenting PCP will remain eligible). We will randomly assign consenting PCPs and their PACT nurse (if they choose to participate) to receive ISOT versus control after stratifying by PCP type of training (physician versus nurse practitioner/physician assistant) and proportion of patients in PCP's panel receiving opioid prescriptions (high vs low, based on median eligible clinician population). Using a permuted block randomization and maximizing the number of PCPs (clusters) should prevent major uneven distribution of caseload size and unmeasured confounders across the arms and increase precision.⁷² The statistician will perform the randomization prior to patient recruitment. Research assistants will be blind to intervention status of patients and clinicians.

ISOT Team and Training: ISOT is a multifaceted intervention. The individual components of ISOT have been adapted from recommendations made as part of clinical practice guidelines^{11,16}, our preliminary studies, and prior experience in conducting multifaceted intervention studies in primary care.^{48,51} The unique aspect of this intervention is its integration of different treatment recommendations into a single package. This method of treatment development and adaptation is similar to other effective multifaceted interventions.⁷³

A research nurse care manager (NCM) will be hired to participate in this study. The NCM will be employed full-time. S/he will have clinical training as a registered nurse (R.N.) and have a clinical background in chronic disease management and outpatient treatment. The individual will receive extensive training in chronic pain management, prescription opioid safety, and research procedures.

ISOT Intervention Components

Clinician Education and Activation:

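### Outcome staff are described as blind to arm, yet research staff read the medical record before follow-up visits, and no described step keeps ISOT-only entries from them

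*Combined protocol and SAP*

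**What the plan says.** The combined protocol and SAP promises blinding twice. Under Randomization: "Research assistants will be blind to intervention status of patients and clinicians". Under Study Measures: "Research staff collecting outcome data will be blinded to participant and clinician intervention status". The separation of teams described there runs in one direction only: "The ISOT intervention team will not have access to data obtained by the research team", with an exception for patient safety.

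Two chart reviews precede research visits. Under Measures of Prescription Opioid Misuse/Abuse (Aim 1): "Research staff will review medical record data prior to research visits to confirm medication status", after which "Participants will be asked to validate pharmacy data about prescription status". Under Measures of Opioid-Related Adverse Events (Aim 1): "Prior to appointments, research staff will review medical record data for participants to track adverse effects".

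On allocation, the Randomization section states: "We will randomize by PCP; patients will be assigned to intervention or control based on randomization of their PCP and PACT nurse".

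The intervention can write to the same record. Clinician Education and Activation, item e, lists a chart note among the ways the nurse care manager (NCM) may give feedback, depending on clinician preference. System Assessment and Intervention, items a and b, let the NCM place or draft a urine drug test (UDT) order.

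**The concern.** A blinding statement protects results only if the procedure lets staff remain blind. Here a stated step, reading the chart before a follow-up visit, can show staff the arm of the patient they are about to assess. Ratings that involve judgement could then shift with knowledge of arm. The final report would also claim a blinding that the described procedure does not secure.

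Two groups of outcomes are at stake. The first is adverse events, the subject of the second hypothesis under Aim 1. The second, if the same people interview, is the interviewer-administered SCID and Timeline Followback (TLFB). Analyses for Aim 1 lists the SCID as one of three primary outcomes, although Study Measures names the COMM as the primary outcome.

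**Working it through.** The plan gives no figure on this point, so there is none to reproduce. The check sets the sections side by side.

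**1. Does the blinding statement cover the chart review?** For adverse events, yes. Emergency room (ER) visits, falls and overdoses found in the chart are Aim 1 outcome data, so whoever abstracts them is collecting outcomes, whether or not that person also interviews.

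**2. What in the chart could show the arm?**

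| Entry | Arm | Certainty |
|---|---|---|
| NCM chart note | ISOT only | Optional; one of several feedback routes |
| UDT order placed or drafted by the NCM | ISOT only | Optional |
| One-time NCM appointment (Patient Assessment and Activation, item a) | ISOT only | Planned for each ISOT patient; place of recording not stated |
| Prescription monitoring (PDMP) check | Both arms | Recorded in the chart; the Aim 2 power section expects a large difference between arms |

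**3. When?** Visits are at baseline, 6 and 12 months. A patient's own baseline chart should hold no NCM entries, because the NCM works with enrolled patients. The exposure is at months 6 and 12, which is 2 of 3 visits.

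**4. How far does one chart reach?** The sample-size section plans an average of 5 patients per primary care provider (PCP), or 4 after loss. With allocation by PCP, a chart that reveals the arm also reveals it for about 5 − 1 = 4 other patients, or 4 − 1 = 3.

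**5. Is there a second route?** The extraction under Processes of Care Measures (Aim 2) is done as each patient finishes. Other patients of the same PCP may still be in follow-up.

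**6. What stands in the way?** Two protections are described. The ISOT team is kept from research data, and research UDTs carry a study number. Neither stops research staff from seeing ISOT entries in the chart. No restricted view, separate abstractor, rule on the order of review and interview, or check of blinding is described.

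**7. Which outcomes are exposed?**
- Adverse-event ascertainment: exposed in either case. Study Measures lists ER visits without qualification, while Analyses for Aim 1 counts only those related to pain. No rule for relatedness is given, and the plan does not say who judges it. Few events are expected and Fisher's exact test is planned, so a few differently classified events could matter.
- SCID and TLFB: exposed if chart reviewers also interview.
- COMM (self-report) and research UDT (laboratory): less exposed. Chart-confirmed medication status may still bear on which UDT results count as unexpected.

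**The case against.** The strongest reply is that the documents are silent rather than contradictory. The term for chart reviewers is simply research staff. Nothing says that they open NCM notes or that they are the interviewers. Every ISOT-only trace is optional, or its recording is unstated. The opening page refers the reader to a publication for final protocol details, and a masking step could be described there. The COMM is not interviewer-rated.

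Most of this stands, and it limits the point to possible unblinding. It does not remove the point: adverse-event review is outcome collection whoever does it, and these documents supply no safeguard.

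A further objection is that patients can mention the NCM in the interview, so chart restriction alone cannot guarantee blindness. That is right, and the fix has to allow for it.

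A reader might infer that PDMP checks virtually identify the arm, since the Aim 2 power section gives a current query rate of 3-5% and expects a large difference. The documents do not support a figure for this. The 17-21 points quoted there are a detectable difference on binary outcomes, tabulated in Table 2 for UDT against a 40% control rate. They are not a PDMP forecast, and the control rate after the workshop is not given. Even if 17-21 points are borrowed with equal arms, guessing ISOT when a check is present and control otherwise is right 0.5 + d/2 of the time: 0.5 + 0.17/2 = 58.5% to 0.5 + 0.21/2 = 60.5%, against 50% by chance. A larger difference would raise this, but its size is not stated. PDMP entries are one more clue and no basis for an estimate.

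**Conclusion.** The point holds as a gap between a stated property of the trial and a stated procedure. Blind outcome collection is not secured for adverse-event abstraction at months 6 and 12. It is not secured for the SCID and TLFB either if reviewers interview. This is worth changing because the main remedy is cheap.

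A reader might go further and infer that blinding failed or that the results are biased. The documents show neither. They do not establish that ISOT entries were made in any given chart, that reviewers saw them, or that ratings moved. No size of bias can be derived.

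The conclusion rests on two assumptions: that no masking step exists outside these documents, and that the pre-visit review gives access to notes or orders and not only to medication and encounter fields.

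**What to change.** 1. **Medication status.** Before each follow-up visit, anyone who interviews sees only a structured pharmacy list of drugs and dates, with no notes, orders or PDMP entries. Participants validate it as already planned.
2. **Adverse events.** Those staff open the chart for events only after that visit's SCID, TLFB and participant event questions are complete. A chart opened after month 6 could still inform the month-12 interview or interviews with the same PCP's other patients. So take ER visits and overdoses from structured encounter data where possible. Hold the process-of-care extraction until that PCP's patients have finished their month-12 interviews, or give it to existing staff who do not interview them.
3. **Classification.** Reconcile the two definitions of ER visits, fix the relatedness rule in advance, and classify events from extracts with NCM entries and arm removed.
4. **Reporting.** Record any unblinding, including disclosure by patients. Describe blinding as intended for interviewers and not assured for chart abstraction. If data collection is over, items 3 and 4 still apply as far as the data allow, with a statement of who reviewed charts.

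**Cost.** This is mainly re-ordering of planned tasks. Data access is described for identifying eligible patients and may need extending to pre-visit medication lists. Staff numbers are not given, so any option using non-interviewing staff depends on staffing. Chart and self-reported events are reconciled after the visit instead of at it, and event counts may arrive slightly later. If the pre-visit review also serves safety oversight, keep that use through staff who do not interview.
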